9.7.1.2 Efficacy evaluation

9.7.1.2.1 Analysis of the primary variable(s)

The primary objective is to evaluate if a dose dependent reduction in MSBP exists when comparing two doses of valsartan solution (0.25 mg/kg and 4 mg/kg) over a 6 week period in children 1-5 years old with hypertension (MSBP \geq 95th percentile for age, gender and height), with or without CKD.

The primary efficacy variable is change from baseline (Visit 2) in mean systolic blood pressure (MSBP) at Week 6 endpoint during the double-blind period 1. The primary analysis will be performed on the FAS.

Statistical hypothesis, model, and method of analysis

The null hypothesis is that there is no treatment difference in the reduction of MSBP (mmHg) between dose groups 0.25mg/kg (low) and 4 mg/kg (high). The alternative hypothesis is that there is a difference between dose groups 0.25 mg/kg and 4 mg/kg. The hypotheses were expressed as follows:

$$H_0: \delta_{\text{low}} = \delta_{\text{high}} \text{ versus } H_1: \delta_{\text{low}} \neq \delta_{\text{high}}$$

where δ s are the mean changes from baseline at Week 6 endpoint in MSBP in the treatment group indicated.

The treatment comparison will be tested at a two-sided significance level of 0.05. The change from baseline in MSBP at Week 6 endpoint during double-blind phase will be analyzed in the FAS using an analysis of covariance model (ANCOVA) as the primary analysis model with treatment and CKD strata as factors and baseline MSBP as the covariate. The baseline MSBP values will be centered by subtracting the overall mean of all patients included in the analysis for FAS. For patients with missing values at Week 6, the last post-baseline observation during the double-blind period will be carried forward (LOCF) as the Week 6 endpoint. CKD strata (yes/no) are the stratification factor used for IRT randomization. When the investigator entered a wrong stratification stratum in IRT, a protocol deviation (PD code = S01) is registered and the correct stratification factor is used for all analyses. The estimated treatment difference for the treatment comparison will be tabulated along with the associated 95% confidence interval and two-sided p-value. Treatment by baseline MSBP interaction will be examined by adding the treatment-by-baseline-MSBP term to the primary analysis model. The results of this assessment will be presented in the CSR section 16.1.9.

Supportive analyses

In addition to the primary analysis based on the FAS population, a similar analysis for the primary endpoint will also be performed on the PPS population as a supplementary assessment.

To further assess the dose response, the change from baseline at Week 6 endpoint in MSBP will be analyzed in FAS by an analysis of covariance model with CKD strata as the factor and baseline MSBP as a covariate, and dose per body weight (mg/kg) as the main regressor. The estimated slope with 95% confidence interval and p-value for the dose per body weight will be provided.

Subgroup analysis for CKD/non CKD patients

Similar analysis of the primary efficacy variable for the treatment comparison will be performed for the subgroup of CKD patients and for the subgroup of non-CKD patients (per CKD yes/no strata). The estimated treatment difference, 95% confidence interval and two-sided p-value for the treatment comparison within each subgroup analysis will be provided. Furthermore, treatment-by-CKD strata interaction in the entire FAS will be assessed by inclusion of the additional interaction term to the primary analysis model for the overall analysis in FAS and the p-value for the respective interaction term will be provided.

Descriptive statistics

The change from baseline in MSBP (together with the corresponding baseline and post-baseline MSBP) during double-blind phase will be summarized by treatment and visit (including Week 6 LOCF endpoint) for the FAS (for overall as well as for each of the CKD/non-CKD subgroup). The MSBP will be plotted versus visit (not including Week 6 LOCF endpoint) by treatment group for the FAS (for overall as well as for each of CKD/non-CKD subgroup). In addition, change from baseline in MSBP will also be plotted versus visit by treatment group for the FAS (for overall as well as for each of CKD/non-CKD subgroup).

9.7.1.2.2 Analysis of secondary variable(s)

The two-sided 0.05 significance level and 95% confidence interval will be provided for the following analyses as applicable. The analyses described below will be carried out in FAS for the double-blind period 1 and in OFAS for the open-label period 2.

Period 1

Change from baseline in mean diastolic blood pressure (MDBP)

Similar analysis as for MSBP will be performed for MDBP to evaluate the reduction of MDBP from baseline. Change from baseline at Week 6 endpoint in the double-blind period (using LOCF) in MDBP will be analyzed for FAS patients using an analysis of covariance (ANCOVA) model with treatment and CKD strata as factors and baseline MDBP as the covariate. Treatment comparison will be performed at the two-sided significance level of 0.05. The estimated treatment effects, treatment difference, 95% confidence interval, and p-value for the treatment comparison will be provided. In addition, similar supportive analysis for PPS will be also provided.

Similar summary statistics and plots as for MSBP will be provided for change from baseline in MDBP.

Percentage of patients achieving MSBP < 90th percentile for age, gender and height

Percentage of patients achieving MSBP < 90th percentile for age, gender and height at Week 6 endpoint will be analyzed using a logistic regression model with treatment and CKD strata as

factors and baseline MSBP as the covariate. The odds ratio of Valsartan 4.0 mg/kg / Valsartan 0.25 mg/kg will be computed, along with the associated 95% confidence interval and p-value. In addition, the number and % of patients achieving MSBP < 90th percentile for age, gender and height will be summarized by treatment and visit (including the Week 6 endpoint). Similar analyses will be carried out for the CKD and non-CKD subgroups of patients.

Percentage of patients achieving MSBP < 95th percentile for age, gender and height

Percentage of patients achieving MSBP < 95th percentile for age, gender and height at Week 6 endpoint will be also analyzed using a logistic regression model with treatment and CKD strata as factors and baseline MSBP as the covariate. The odds ratio of Valsartan 4.0 mg/kg / Valsartan 0.25 mg/kg will be computed, along with the associated 95% confidence interval and p-value. In addition, the number (and %) of patients achieving MSBP < 95th percentile for age, gender and height will be summarized by treatment and visit (including the Week 6 endpoint). Similar analyses will be carried out for the CKD and non-CKD subgroups of patients.

Percentage of patients achieving both MSBP and MDBP < 90th percentile for age, gender and height; percentage of patients achieving both MSBP and MDBP < 95th percentile for age, gender and heights.

Percentage of patients achieving both MSBP and MDBP < 90th percentile for age, gender and height at Week 6 endpoint will be analyzed using a logistic regression model with treatment and CKD strata as factors and baseline MSBP as the covariate. The odds ratio of Valsartan 4.0 mg/kg / Valsartan 0.25 mg/kg will be computed, along with the associated 95% confidence interval and p-value. In addition, the number (and %) of patients achieving both MSBP and MDBP < 90th percentile for age, gender and height will be summarized by treatment and visit (including the Week 6 endpoint). Similar analyses will be carried out for the CKD and non-CKD subgroups of patients.

Similar analyses will be also performed for the percentage of patients achieving both MSBP and MDBP < 95th percentile for age, gender and height at Week 6 endpoint.

UACR (Urine Albumin Creatinine Ratio) in CKD patients

UACR was collected for CKD patients only. The UACR value at a given visit for a patient is to be derived by the median of the three lab values collected for that visit. The UACR value will be assessed in the CKD patients.

Change from baseline in log(base 10)-transformed UACR will be analyzed using an ANCOVA model with treatment as a factor and log (base 10)-transformed baseline UACR as a covariate. The estimated treatment effects, treatment difference, 95% confidence interval, and p-value for the treatment comparison will be provided. The estimates to be presented will be in back-transformed scale.

Instead of the specified % change from baseline in UACR $\leq 25\%$ in the protocol, the UACR response is to be defined as a percentage reduction from baseline in UACR $\geq 25\%$. The proportion of patients with UACR response at Week 6 endpoint (LOCF) will be analyzed using a logistic regression with treatment as a factor and baseline UACR as a covariate. The odds ratio of Valsartan 4.0 mg/kg / Valsartan 0.25 mg/kg will be computed, along with the associated 95% confidence interval and p-value.

Summary statistics (n, mean, standard deviation, median, min, max, geometric mean) of the UACR values for baseline, Week 6 endpoint and the respective change (from baseline at Week 6 endpoint) will be provided by treatment group. The number and percent of patients will be summarized by treatment group for each of the following categories in change from baseline at Week 6 endpoint: $\geq 25\%$ reduction, change is less than 25% in positive/negative direction, and $\geq 25\%$ increase. Similar summary will be also provided by treatment group for the following categories: $\geq 50\%$ reduction, change is less than 50% in positive/negative direction and $\geq 50\%$ increase.

Cystain C GFR (Glomerular filtration rate) in CKD patients

cGFR (Cystain C GFR) was collected and assessed for CKD patients only.

Change from baseline in log(base 10)-transformed cGFR will be analyzed using an ANCOVA model with treatment as a factor and log(base 10)-transformed baseline cGFR as a covariate. The estimated treatment effects, treatment difference, 95% confidence interval and p-value for the treatment comparison will be provided. The estimates to be presented will be in back-transformed scale.

Summary statistics (n, mean, standard deviation, median, min, max, geometric mean) of the cGFR values for baseline, Week 6 endpoint and the respective change (from baseline at Week 6 endpoint) will be provided by treatment group.

Period 2

The efficacy data during the open-label period 2 will be assessed based on the summary statistics and plots below in OFAS. The summaries and plots will be presented with one single arm including all patients evaluated in the open-label period 2.

1. Change from baseline (Visit 2) in MSBP (together with the corresponding baseline and post-baseline MSBP) will be summarized (with n, mean, standard deviation, median, min, and max) by visit (including LOCF endpoint at end of the open-label period 2) during the open-label period 2. Similar summary will be provided for MDBP. Similar summaries for MSBP and MDBP will also be provided for the CKD and non-CKD subgroups. In addition, similar plots as for MSBP/MDBP in the double-blind period will be provided with one single arm for the OFAS in the open-label period 2.
2. Percentage of patients achieving MSBP $< 90^{\text{th}}$ percentile (as well as MSBP $< 95^{\text{th}}$ percentile, both MSBP/MDBP $< 90^{\text{th}}$ percentile, and both MSBP/MDBP $< 95^{\text{th}}$ percentile) for age, gender and height will be summarized by visit during the open-label period 2.

label period 2. In addition, similar summaries will be provided for the CKD and non-CKD patients

3. In the CKD patients, change from baseline in UACR (together with the corresponding baseline and post-baseline UACR) will be summarized (with n, mean, standard deviation, median, min, max and geometric mean) by visit during the open-label period 2. In addition, the n and percentage of CKD patients in the categories of UACR changes (as defined in the assessment during the period 1) will be provided by visit during the open-label period 2.
4. In the CKD patients, change from baseline in cGFR (together with the corresponding baseline and post-baseline cGFR) will be summarized (with n, mean, standard deviation, median, min, max and geometric mean) by visit during the open-label period 2.

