2.2 Secondary objectives

- To assess the efficacy of valsartan in reducing the mean diastolic blood pressure (MDBP) in children with hypertension.
- To assess the efficacy of valsartan in controlling the MSBP and MDBP in children with hypertension. The target mean BP is $<90^{\text{th}}$ percentile for age, gender and height.
- To assess the safety and tolerability profile of valsartan in children with hypertension, with or without CKD.
- To assess the effect of valsartan on proteinuria and eGFR in a subset of children with hypertension and CKD.

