4.1 Inclusion criteria

Patients eligible for inclusion in this study have to fulfill all of the following criteria:

1. Written informed consent must be obtained before any assessment is performed.
Parent(s)/guardian(s) have to provide consent in writing (written informed consent) after the purpose and nature of the study has been clearly explained to them.
2. Male or female, 1 to 5 years at baseline (visit 2), with a documented diagnosis of hypertension ([National High Blood Pressure Education Program 2004](#))
3. CKD patients must be defined as any of the following criteria ([Hogg et al 2003](#)) (At least 50% of enrolled patients will be CKD-patients):
 - a. Kidney damage for ≥ 3 months, as defined by structural or functional abnormalities of the kidney, with or without decreased GFR, manifested by one or more of the following features:
 - Abnormalities in the composition of urine
 - Abnormalities in imaging tests
 - Abnormalities on kidney biopsy
 - b. Estimated GFR < 60 mL/min/1.73m² (calculated by Modified Schwartz Formula) for ≥ 3 months, with or without the other signs of kidney damage described above.
4. MSBP (mean of 3 measurements) must be $\geq 95^{\text{th}}$ percentile, and $\leq 25\%$ above the 95^{th} percentile, for age, gender and height, at baseline (visit 2) ([Appendix 2](#)), by office automatic blood pressure monitor and cuff, provided by the Sponsor. Confirmation of MSBP $\geq 95^{\text{th}}$ percentile must be made using the auscultatory blood pressure method.
5. Able to swallow the valsartan solution
6. Body weight must be ≥ 8 kg and ≤ 40 kg at baseline
7. Must be able to safely washout prior ARB, ACEi and DRI therapy (if applicable) and other antihypertensive therapy (if applicable)

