Appendix 2: Pediatric blood pressure tables and growth charts

Blood pressure percentiles will be determined with the below BP tables which were published by the *National High Blood Pressure Education Program Working Group on High Blood Pressure in Children and Adolescents* ([NHBPEP Fourth Report 2004, Lurbe 2009](#)).

Height percentiles will be determined with below growth charts published by *Centers for Chronic Disease Control and Prevention* (<http://www.cdc.gov/growthcharts>).

Using the tables

Use the correct gender growth chart to determine the height percentile.

Measure and record the child's MSBP and MDBP.

Use the correct gender table for SBP and DBP.

Find the child's age on the left side of the table. Follow the age row horizontally across the table to the intersection of the line for the height percentile (vertical column).

There, find the 50th and 95th percentiles or values for 20% and 25% above 95th percentile for SBP in the left columns and for DBP in the right columns.

[figure not shown]
Special methods and scales

Birth to 36 months: Girls

Length-for-age and Weight-for-age percentiles

NAME _____

RECORD # _____

Published May 30, 2000 (modified 4/20/01)

SOURCE: Developed by the National Center for Health Statistics in collaboration with the National Center for Chronic Disease Prevention and Health Promotion (2000). <http://www.cdc.gov/growthcharts>

[figure not shown]
SAFER • HEALTHIER • PEOPLE™

2 to 20 years: Girls

Stature-for-age and Weight-for-age percentiles

NAME _____

RECORD # _____

Published May 30, 2000 (modified 11/21/00).

SOURCE: Developed by the National Center for Health Statistics in collaboration with
the National Center for Chronic Disease Prevention and Health Promotion (2000).
<http://www.cdc.gov/growthcharts>

[figure not shown]

SAFER • HEALTHIER • PEOPLE™

Birth to 36 months: Boys Length-for-age and Weight-for-age percentiles

NAME _____

BECOBD # _____

Published May 30, 2000 (modified 4/20/01).

[figure not shown]
SOURCE: Developed by the National Center for Health Statistics in collaboration with the National Center for Chronic Disease Prevention and Health Promotion (2000). <http://www.cdc.gov/growthcharts>

SAFER • HEALTHIER • PEOPLE™

2 to 20 years: Boys
Stature-for-age and Weight-for-age percentiles

NAME _____
RECORD # _____

Published May 30, 2000 (modified 11/21/00).

SOURCE: Developed by the National Center for Health Statistics in collaboration with

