The severity codes of PDs causing subjects to be excluded from analysis set are recorded in the latest version of VAP M3 document. Protocol deviations (with and without leading to exclusion from analysis sets) will be summarized during the double-blind period for RAN and also during the open-label period 2 for the randomized patients who entered the open-label period 2.

For RAN, summary statistics will be provided by treatment group for demographics and other baseline characteristics including age, height, weight, BMI, head circumference, MSBP (mean systolic blood pressure), MDBP (mean diastolic blood pressure), pulse, as continuous variables and gender, race, ethnicity, continuing use of prior antihypertensive treatment

(Yes/No), CKD (chronic kidney disease) /non-CKD as qualitative variables. Comparisons of treatment groups with respect to the demographics and baseline characteristics will be performed using chi-square tests or a t test as appropriate. The results of these tests are provided for descriptive purposes, and will not be used as a formal basis to determine the factors to be included in statistical models.

Relevant medical history and current medical conditions will be summarized by treatment group for RAN.

Study drug exposure in Period 1 (double-blind phase):

Duration (in days) of exposure to study drug in Period 1 will be computed and summarized by treatment group(for all patients as well) for SAF as follows.

last study drug date in Period 1 – study drug start date in Period 1+ 1,

or

last visit date in Period 1 – study drug start date in Period 1 if the last study drug date in Period 1 is missing or incomplete.

Study drug start date in Period 1 is Visit 2 date. Last study drug date in Period 1 is the last known study drug date from the study phase completion panel.

Study drug exposure in Period 2 (open-label phase):

Duration (in days) of exposure to study drug in period 2 will be summarized by each dose, i.e. 1 mg/kg, 2 mg/kg, 3 mg/kg, 4 mg/kg (and non-protocol defined dose, if any) as well as total exposure on any dose for OSAF as follows.

The total study drug exposure to any dose in Period 2 is calculated as below:

Last study drug date in Period 2 – study drug start date in Period 2 +1

or

last visit date in Period 2 – study drug start date in Period 2 if the last study drug date in Period 2 is missing or incomplete.

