10.3 Sample SAS program for efficacy analyses

The SAS code provided is intended to reflect the type of analyses planned; however, the actual code used may not be a verbatim of this example. The variable names used in this code were selected for understanding of the methodology and do not necessarily reflect the actual variable names in the data.

ANCOVA model for primary analysis

For the ANCOVA model in the analysis of change from baseline in MSBP at Week 6, the following SAS code are used:

```
PROC MIXED DATA=eff;
  CLASS treatment CKD;
  WHERE population = population (FAS);
  MODEL response= treatment CKD baseline_MSBP;
  ESTIMATE 'Valsartan High dose vs. Valsartan Low dose' treatment 1 -1/CL;
  run;
```

- “eff” denotes the efficacy data set containing individual observations for the change from baseline in MSBP
- “treatment” denotes the variable containing the treatment groups (Low, High)
- “CKD” denotes the variable containing the CKD strata (CKD and non-CKD)
- “baseline_MSBP” denotes the centered baseline variable containing individual patient baseline MSBP deviation from the mean of all FAS patients.

Logistic regression model

The SAS procedure MIXED is used with the following SAS code:

```
proc logistic data=eff;
  class treatment CKD/(param=ref ref='Low');
  model response = trt base;
  contrast 'High dose vs. Low dose' treatment 1 -1 / estimate=exp;
run;
```

where `y`, `region`, `trt`, and `base` denote control or response variable, region, treatment, and baseline value (msSBP, or msDBP for `y` involving only msDBP) respectively.

The odds ratio of High dose /Low dose will be computed, along with associated 95% confidence intervals.

Comparability of baseline characteristics

Baseline comparability between the three treatment groups, for continuous parameters, was tested using two-sample t-test:

```
proc ttest;  
  class treatment;  
  variable <Quantitative baseline variable>;  
run;
```

Baseline comparability between treatment groups, for categorical parameters, was tested using a CMH chi square-test:

```
proc freq ;  
  tables treatment* <Qualitative baseline variable > / cmh noprint;  
  output out=<output dataset> cmhga;  
run;
```

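### Joint systolic and diastolic control is adjusted for baseline MSBP only; adding baseline MDBP to the two full-FAS models is a cheap, optional improvement

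*SAP*

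**What the plan says.** SAP 9.7.1.2.2 (Period 1) defines two joint control endpoints. For the first: "Percentage of patients achieving both MSBP and MDBP < 90th percentile for age, gender and height at Week 6 endpoint will be analyzed using" logistic regression, with treatment and CKD strata as factors and baseline MSBP as covariate. For the second: "Similar analyses will be also performed for the percentage of patients achieving both MSBP and MDBP < 95th percentile for age, gender and height", so the same model applies by reference. Both are repeated in the CKD and non-CKD subgroups, which makes six fits. None includes baseline MDBP.

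Other places bear on this:

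- The MDBP analysis in the same section uses an ANCOVA "model with treatment and CKD strata as factors and baseline MDBP as the covariate".
- SAP 9.7.1.1 lists MDBP among the baseline characteristics to be summarised and compared by arm: "MDBP (mean diastolic blood pressure), pulse, as continuous variables and gender, race, ethnicity".
- The covariate note in SAP 10.3 reads "denote control or response variable, region, treatment, and baseline value (msSBP, or msDBP for" a response that involves diastolic pressure alone. A joint response therefore takes the systolic baseline, in agreement with 9.7.1.2.2.
- Protocol 4.1, criterion 4, begins "MSBP (mean of 3 measurements) must be" and sets a lower and an upper limit on MSBP. It sets none on MDBP.
- Protocol 2.2 has the objective "To assess the efficacy of valsartan in controlling the MSBP and MDBP in children with hypertension". Protocol 9.5.1 lists only MSBP <90th percentile as the control variable, so the joint endpoints are SAP additions.

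**The concern.** MDBP is one of the two components of each joint outcome, and its baseline is likely to predict whether a child meets the diastolic part at Week 6. Because entry restricts MSBP only, baseline MDBP may lie anywhere relative to its threshold, and the arms may differ on it by chance.

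Two things are at stake. A chance diastolic imbalance passes unadjusted into the odds ratio. Some power may also be lost if diastolic control is often what decides the outcome. Both concern secondary results that come closest to the protocol's objective of controlling both pressures.

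**Working it through.** **1. Stated figures.** The documents give no power or precision figure for these endpoints; Protocol 9.8 marks power for key secondary variables as not applicable. The stated inputs are 116 completers (58 per arm), 130 randomised (65 per arm), SD 11 mmHg for MSBP change, a 6 mmHg difference and two-sided 0.05. For the primary endpoint, 6/(11 × √(2/58)) = 2.94 and Φ(2.94 − 1.96) = 83.6% (83.0% with the t distribution). The claim of at least 80% stands, but says nothing about joint control.

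**2. Assumed inputs.**

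- Baseline MSBP exceeds the 95th percentile by an exponential amount, mean 7 mmHg, capped at 25%.
- Mean baseline MDBP is −12, −6, 0 or +4 mmHg from its 95th percentile, SD 9-10.
- Systolic-diastolic baseline correlation is 0.3 or 0.5; the slope of Week 6 on baseline MDBP is 0.4-0.7; MDBP change SD is 9; error correlation is 0.6.
- The systolic effect is 6 or 8 mmHg and the diastolic effect 3-5 mmHg.
- Half have CKD, with no CKD effect. There is no dropout.
- Thresholds come from Protocol Appendix 2. The 90th percentile is interpolated assuming normality: P90 = P50 + (1.282/1.645) × (P95 − P50).

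These give joint control <90th of 21-41% (low dose) against 43-61% (high dose), and <95th of 34-54% against 59-73%.

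**3. Models compared.** Planned: logit(p) = treatment + CKD + baseline MSBP. Alternatives: the same plus MDBP in mmHg, or plus MDBP minus the child's own 95th percentile. There were 24 cases (six scenarios, two endpoints, N = 116 and 130), with 16,000 simulated trials per scenario and N, and a paired simulation error of 0.1-0.2 points.

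| | MDBP in mmHg | MDBP as distance |
|---|---|---|
| Power change, all cases | −0.2 to +2.1 points | −0.1 to +3.7 points |
| Power change, mean MDBP 0-4 mmHg above the 95th percentile | +0.6 to +2.1 | +1.4 to +3.7 |
| Rise in SE of log odds ratio | 0.6-3.9% | 0.6-6.3% |
| Shift in median log odds ratio | +0.01 to +0.08 | +0.01 to +0.12 |
| Overall false positives (planned model 4.7-5.3%) | 4.8-5.3% | 4.9-5.4% |

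With mean MDBP 6-12 mmHg below the 95th percentile, the power change is −0.2 to +0.5 points across both forms. The largest gain is 78.3% to 82.0%. The null cases used 40,000 trials each.

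**4. Why power can rise while the interval widens.** In a second set of simulations (N = 130, <90th, mean MDBP 3 mmHg above the 95th percentile, slope 0.6, 4000 trials), the average log odds ratio and SE go from 0.948 and 0.392 to 0.995 and 0.405. The ratio rises from 0.948/0.392 = 2.42 to 0.995/0.405 = 2.46, and power from 68.6% to 70.4%. The 95% half-width goes from 1.96 × 0.392 = 0.77 to 1.96 × 0.405 = 0.79. The estimate moves away from zero slightly faster than its SE grows.

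**5. Sensitivity.** With a deliberately strong predictor (slope 0.8, residual SD 5), power at <90th goes from 71.8% to 76.1% (mmHg) or from 70.7% to 77.6% (distance, separate run). The SE rises by 7% and 11%.

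**6. Chance imbalance.** The SE of the between-arm difference in distance runs from 9 × √(2/65) = 1.58 to 10 × √(2/58) = 1.86 mmHg. A difference of at least 2 mmHg then has probability 21-28%, as simulated. When it favours the high dose (10-14% of trials), false positives for the high dose, nominally 2.5%, are 2.7-5.5% as planned, 2.9-4.0% with mmHg and 2.2-2.7% with distance. When it goes the other way they are 0.8-2.6%, 1.5-2.3% and 2.0-2.9%.

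**7. Responders per model term, least favourable case (<90th, 21% against 43%).** Full FAS: 58 × 0.21 + 58 × 0.43 ≈ 37 responders, or about 12 per term with three terms and 9 with four. A subgroup of 58: about 18, or about 6 per term if MDBP were added to treatment and MSBP. No full-FAS fit failed to converge.

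**The case against.** The strongest case against is that this is a preference. SAP 9.7.1.2.2 and 10.3 agree with each other, the test is valid, and the joint endpoints are not in the protocol's list of secondary variables. Baseline MDBP is compared by arm and adjusted for in its own ANCOVA, so an imbalance would be visible. The size of any gain depends entirely on assumed inputs. The conditional false-positive figures also favour the distance covariate by construction, because trials are selected on imbalance in that same quantity. All of this stands, and it is why the point is optional.

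Two further costs stand. Odds ratios are non-collapsible, so the full-FAS joint odds ratio would no longer be directly comparable with the subgroup odds ratios or the MSBP-only ones. The full-FAS model would also have fewer responders per term.

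What does not follow is that nothing should change. Seeing an imbalance in a baseline table does not remove it from the odds ratio, and a covariate added after unblinding would be open to challenge.

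A reader might infer more than the documents support:

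- *That the planned analysis is wrong or inflates false positives.* The overall rate is nominal; the raised rate in one subset of trials is offset in its mirror image.
- *That adjustment would tighten the interval.* It widens slightly in all 24 cases.
- *That baseline MDBP belongs in all six fits.* Responders in the subgroups may be too few.

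**Conclusion.** The omission is real and stated; it is an improvable choice, not an error. For the two full-FAS joint-endpoint models, adding baseline MDBP gives a power change of about nil if mean baseline MDBP is 6-12 mmHg below its 95th percentile, and about +1 to +4 points if it is at or up to 4 mmHg above. A larger gain (4-7 points) appeared only when baseline MDBP was assumed to be very prognostic. Adjustment also limits how far a chance diastolic imbalance moves the odds ratio, most clearly when MDBP enters as distance from threshold.

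The direction is well supported. The size is uncertain, because the documents give no baseline MDBP distribution, diastolic SD, diastolic effect or control rates. The primary analysis is not affected.

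**What to change.** Before unblinding:

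1. In SAP 9.7.1.2.2, add baseline MDBP as a second covariate in the full-FAS logistic models for joint control <90th and <95th. Prefer baseline MDBP minus the child's own 95th percentile for age, gender and height. Raw mmHg partly reflects age: the diastolic 95th percentile in Appendix 2 runs from 54 to 74 mmHg over ages 1-5. The values are already tabulated, "above 95th percentile for SBP in the left columns and for DBP in the right columns". Raw mmHg is acceptable.
2. Keep the CKD and non-CKD subgroup fits with baseline MSBP only, and say so.
3. In SAP 10.3, state that the full-FAS joint-endpoint models carry both baselines and that the subgroup fits carry baseline MSBP only. A general statement about any response involving both pressures would pull MDBP into the subgroup fits as well.
4. In the sample MODEL statement, which has one baseline term and no CKD term, add the second baseline for these fits and the planned CKD factor.

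The work is one covariate in two of six fits, plus edits to one note and one line of sample code. No new data are needed. Downsides to state in the SAP:

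- The SE of the log odds ratio rises by about 1-6%, more if MDBP is very prognostic.
- The conditional odds ratio moves slightly further from 1.
- The full-FAS joint odds ratio is not directly comparable with the subgroup or MSBP-only odds ratios.
- There could be about 9 responders per model term at <90th in the least favourable assumed case.
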